#### **4.13.5 Confidentiality**

The signed version of the consent form will be stored in a separate file from de-identified, coded research records. A unique study ID code will be assigned to the subject. Study data will be entered in an electronic CRF which will identify the participant only by a unique study ID code. Consults and results collected from diagnostic tests will be de-identified by removing the patient name, date of birth, hospital ID number and any other identifying PHI. These will be replaced with the patient's unique study ID code. All hard copies of data will be stored in a locked filing cabinet, only accessible by the study investigator and his/her research team. Electronic data will be entered on a central database stored on a secure computer network that is password protected. The master file that links the subject to the unique study ID code will be stored electronically at each study site in a separate folder on a password protected computer on a secure institutional network. No personal identifiers will leave the study sites.

#### **4.13.6 Protocol amendments**

Any protocol amendments will be communicated to the REB/IRB, co-investigators, and PIs at other study sites. Amendments will require ethics approval from coordinating and local site before implementation.

#### **4.13.7 Declaration of conflict of interest**

All investigators declare no conflict of interest.

### **5. VISIT SCHEDULE AND PROCEDURES**

Consenting patients will be followed up clinically by their regular physician (e.g. Cardiologist, Internist, other physician) in collaboration with their local site-PIs, in accordance with the 2022 ACC/AHA standard of care guidelines for the management of myocarditis.

Patients will be followed at 3 months and 12 months after diagnosis and annually thereafter for up to 3 years. To standardize follow-up timing the date of vaccination will be assigned as the baseline date. However, baseline visit data will be collected from initial presentation and medical contact which is usually the date of diagnosis. This distinction is made because there is a variation between cases in date of vaccination to date of diagnosis/initial presentation.

The case report form variable list (Appendix 7) outlines the essential elements to be collected including demographic data, vaccination status, presenting symptoms, physical examination findings, diagnostic testing (routine laboratory work, electrocardiogram, MRI), treatments, and patient outcomes. Quality of life, depression, anxiety, and physical activity will be measured at baseline, 3 months, 12 months, and annually thereafter using validated instruments: quality of life EQ-5D-5L questionnaire for adults or EQ-5D-Y questionnaire for children; depression PHQ-9 and anxiety GAD-7; physical activity International Activity Questionnaire. These will be conducted at clinical visits or by telephone if no concurrent clinical visit is scheduled.

Baseline data will be collected for all etiologies of myocarditis, but thereafter follow-up visits will only be undertaken for patients with vaccine associated myocarditis/pericarditis, COVID-19 myocarditis/pericarditis, and MIS-C/A myocarditis/pericarditis (i.e. not alternative etiology myocarditis).

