## 4.5 Inclusion criteria

### 4.5.1 Inclusion criteria for vaccine associated myocarditis/pericarditis.

1. COVID-19 vaccination within previous 42 days.

AND

2. At least one cardiac symptom of suspected myocarditis/pericarditis (Appendix 5).

OR

At least two non-specific symptoms (Appendix 5).

OR

In infants and young children, at least two non-specific pediatric symptoms (Appendix 5).

OR

No symptoms, but abnormal histopathology or a combination of abnormal cardiac biomarkers with abnormal cardiac imaging (echo or MRI).

AND

3. At least one of the following objective findings (Brighton Criteria case definitions, Appendices 1 to 5):
  - a. Histopathologic examination of myocardial tissue (autopsy or endomyocardial biopsy) showed myocardial inflammation.
  - b. Elevated myocardial biomarker (Troponin T, Troponin I, or CK-MB).
  - c. Cardiac MRI abnormality.
  - d. Echocardiographic abnormality.
  - e. New or worsening arrhythmia on electrocardiogram, Holter monitor, or telemetry.
  - f. Elevated inflammation biomarkers: ESR, CRP, hs-CRP, or D-Dimer.
  - g. Physical examination pericardial friction rub or pulsus paradoxus.
  - h. Pericardial fluid or inflammation by imaging (echo, MRI, or CT).
  - i. Enlarged heart on chest radiograph.

AND

4. No alternative cause of presentation. e.g. infectious or autoimmune myocarditis.

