#### **4.10 Retrospective chart review**

The retrospective study will identify previous cases of vaccine associated myocarditis/pericarditis, COVID-19 associated myocarditis/pericarditis, MIS-C/A myocarditis/pericarditis, and alternative etiology myocarditis.

Recruiting clinicians will refer patients presenting with myocarditis/pericarditis since December 1, 2020 to research staff (i.e., the date Health Canada approved the first mRNA vaccine for COVID19). Initial chart review to determine eligibility for the study and subsequent chart review for initial presentation and follow-up time points will be completed. As vaccination for COVID-19 and COVID-19 infections are occurring continually, chart review of eligible patients will follow the same structure as patients identified from December 1, 2020.

The same clinical information as the prospective study will be collected, including presentation, clinical bloodwork, and cardiac imaging. No data will be collected for the purposes of this study that has not already been collected as part of routine follow-ups. Only available data will be extracted. Follow-up data will be extracted from charts using standardized chart extraction forms at 3 months, 12 months, and annually for up to 3 years following the date of diagnosis of vaccine associated myocarditis/pericarditis, COVID-19 myocarditis/pericarditis or MIS C/A myocarditis/pericarditis.

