## **5.2 Schedule for remote (previous) cases**

Cases of previous myocarditis and pericarditis will be identified from chart review using the same criteria as new cases. For example, if a patient case is out of the immediate post-diagnosis window or their experience of myocarditis/pericarditis occurrence more than 12 months ago, we will extract relevant information for Brighton diagnostic criteria from chart review. We will review relevant investigations that have already been completed previously rather than repeat delayed testing. These patients will be approached to participate in the surveillance study as outlined previously.

After consent, they will join the study schedule at the nearest scheduled study visit e.g. If diagnosis was 13 months ago, they will join the 12-month visit. Each visit will have a range e.g., 12-month visit range will be 12-15 months. This will allow for health outcomes to be retrieved retrospectively and also collected moving forward from the time of joining the study.

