**7.8 Appendix 8. Schedule of assessment**

Tests/Procedures	Baseline	3 months (+/- 1 month)	12 months (+/- 1 month)	24 months (+/- 1 month)	36 months (+/- 1 month)
Eligibility	x				
Demographics	x				
Diagnosis	x				
Medical history	x				
Hospitalization	x				
COVID-19 infection	x				
Vaccination status	x				
Physical exam	x				
Vital signs	x	x	x		
Clinical symptoms	x				
Medications	x				
Bloodwork	SOC	x ^	x ^		
ECG, Holter, Echo, MRI	SOC	x ^	x ^	x ^	x ^
QOL, EQ-5D-5L	x	x	x	x	x
EQ-5D-Y	x *	x *	x *	x *	x *
PHQ-9	x	x	x	x	x
GAD-7	x	x	x	x	x
International Activity Questionnaire	x	x	x	x	x
Events, concomitant medication	x	x	x	x	x
Outcomes		x	x	x	x

\* questionnaire for children only

^ repeat diagnostic tests if initial test was abnormal

Previous cases will join the study schedule at the nearest scheduled study visit

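### Section 5 counts follow-up visits from diagnosis and, in the next sentence, from vaccination; the permitted lag of up to 42 days exceeds the one-month visit window, so the timing of primary endpoint 3 is not fixed

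*Protocol*

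**What the plan says.** Protocol section 5 gives the visit schedule as "Patients will be followed at 3 months and 12 months after diagnosis and annually thereafter for up to 3 years". The next sentence reads "To standardize follow-up timing the date of vaccination will be assigned as the baseline date". Two explanatory sentences follow: "However, baseline visit data will be collected from initial presentation and medical contact which is usually the date of diagnosis", and then "This distinction is made because there is a variation between cases in date of vaccination to date of diagnosis/initial presentation". Neither says from which date the 3-month and later visits are counted.

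Elsewhere:

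- Section 4.10 extracts chart data at 3 months, 12 months and "annually for up to 3 years following the date of diagnosis".
- Section 5.2 places remote cases by diagnosis: "If diagnosis was 13 months ago, they will join the 12-month visit". It gives 12 to 15 months as the range for the 12-month visit.
- Appendix 8 labels the first follow-up column "3 months (+/- 1 month" and uses the same tolerance at 12, 24 and 36 months. It names no time origin.
- Section 3.3 defines primary endpoint 3 (EQ-5D, PHQ-9, GAD-7, activity questionnaire) at baseline, 3 months, 12 months and annually, also without an origin.
- Section 4.5.1 requires "COVID-19 vaccination within previous 42 days" for vaccine-associated cases. Sections 4.5.2 and 4.5.3 do not require vaccination for COVID-19 or MIS-C/A cases, yet section 5 follows these cohorts on the same schedule.

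**The concern.** Adjacent sentences on follow-up timing name different time origins. A site booking a 3-month questionnaire could follow either one and comply with the protocol. The protocol acknowledges that the interval from vaccination to diagnosis varies between patients, but does not say which end of it starts the clock.

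At stake is what the 3-month and later values of primary endpoint 3 mean. If sites choose differently, values carrying the same visit label come from different times since illness. One questionnaire can also be in window under one sentence and out of window under the other. A questionnaire given on the wrong day cannot be re-timed at analysis. For patients whose illness was not preceded by a relevant vaccination, one of the two clocks has no starting point at all.

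**Working it through.** The protocol states no figure to reproduce here; the check is date arithmetic on its own limits.

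**Inputs**

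- Largest lag from vaccination, L: 42 days (section 4.5.1, read as the lag to presentation or diagnosis).
- Visit tolerance: one month either side (Appendix 8).
- Month length: 365.25 / 12 = 30.44 days (an assumption, varied below).

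**Formulas**

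- A visit on day t after diagnosis is day t + L after vaccination. A visit on day t after vaccination is day t − L after diagnosis.
- 3-month target: 3 × 30.44 = day 91.3. Window: 2 × 30.44 to 4 × 30.44, or day 60.9 to day 121.8, a width of 60.9 days.
- Share of one clock's window that also lies in the other's: (60.9 − L) / 60.9.

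**Results at 3 months**

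| Lag L (days) | On target from diagnosis: day after vaccination | On target from vaccination: day after diagnosis | Inside the other window? | Shared part of the windows |
|---|---|---|---|---|
| 0 | 91 | 91 | yes | 100% |
| 7 | 98 | 84 | yes | 89% |
| 14 | 105 | 77 | yes | 77% |
| 28 | 119 | 63 | yes | 54% |
| 42 | 133 | 49 | no | 31% |

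At L = 42:

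- 91.3 + 42 = 133.3, which is 133.3 − 121.8 = 11.5 days after the vaccination-clock window closes.
- 91.3 − 42 = 49.3 (1.6 months), which is 60.9 − 49.3 = 11.6 days before the diagnosis-clock window opens.

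An on-target visit leaves the other window once L exceeds the tolerance, about 30 days. Visits away from target can be affected at shorter lags, as the last column shows.

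**Month length.** With months of 28, 30 and 31 days, an on-target visit at L = 42 falls on day 126, 132 and 135 after vaccination, against upper limits of 112, 120 and 124. The conclusion does not change.

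**Later visits.** Shift and tolerance are both unchanged, so the crossing point is the same. At 12 months and L = 42: 365.25 + 42 = day 407.3 (13.4 months), against an upper limit of 13 × 30.44 = day 395.7. What shrinks is the shift relative to elapsed time: 42 / 91.3 = 46% at 3 months and 42 / 365.25 = 11% at 12 months.

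**A second discrepancy in the windows.** For the 12-month visit, section 5.2 gives 12 to 15 months and Appendix 8 gives 11 to 13 months. Only months 12 to 13 satisfy both.

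**The case against.** The best defence is that section 5 explains itself: vaccination supplies a nominal baseline date, baseline data come from presentation, and the actual visits stay tied to diagnosis, as in sections 4.10 and 5.2. That may be the intention. However, the vaccination sentence gives standardising follow-up timing as its purpose, which is what the preceding sentence had already fixed from diagnosis. The explanation separates the baseline date from baseline data collection and leaves the later visits unaddressed.

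It is also fair to say that the handling of out-of-window readings commonly belongs in the SAP. The protocol has no rule discarding them, so nothing here shows that data would be lost. The time origin itself is different, because sites need it when they book visits.

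A reader might infer four stronger claims that the documents do not support:

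- **That LVEF recovery is distorted.** Primary endpoint 2 has no visit time. It is a gain over the worst baseline value, so relabelling a visit does not change it.
- **That chart-review and prospective data would be pooled on different clocks.** No section puts prospective visits on the vaccination clock alone. Chart review takes only data already recorded in routine care, so the questionnaires would come mainly from prospective visits.
- **That late presenters would look worse because they are seen earlier in a steep recovery.** The protocol gives no recovery curve, so neither direction nor size of bias can be stated.
- **That the problem is confined to 3 months.** The same shift meets the same tolerance at every later visit.

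**Conclusion.** The contradiction stands and no other section resolves it. For lags above about 30 days, an on-target visit by one clock is out of window by the other, by about 12 days at the 42-day limit. This holds at 3, 12, 24 and 36 months.

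The endpoint exposed is primary endpoint 3. Composite MACE has its own clock, 30 and 42 days after vaccination.

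The conclusion rests on the Appendix 8 tolerance and on reading the 42-day limit as the lag to presentation or diagnosis. The number of patients affected cannot be estimated, because no lag distribution is given; for cases diagnosed within a few days of vaccination the effect is slight. Separately, and whatever the lag, a vaccination origin cannot serve COVID-19 or MIS-C/A cases not linked to a vaccination. As a rule for all followed cohorts, the sentence therefore fails as written. It should be corrected, but it does not undermine the study.

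**What to change.** Reconcile sections 4.10, 5 and 5.2 and Appendix 8 to one time origin for the endpoint 3 visits, and state that origin in section 3.3. It should be a single, precisely defined date that exists in every followed cohort. Sections 4.10 and 5.2 and the first visit-timing sentence of section 5 already use the date of diagnosis. Wording that allows either diagnosis or first presentation would reopen the ambiguity, since section 5 says only that the two usually coincide.

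Then:

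- Record that date on the case report form. Appendix 7 lists vaccine dates and a diagnosis date for COVID-19 infection, but its diagnosis row lists only etiology and Brighton level.
- Compute visit windows from it in both chart-review and prospective data.
- Reconcile the 12-to-15-month range in section 5.2 with the one-month tolerance in Appendix 8.
- Keep the vaccination date for the 30- and 42-day MACE endpoint and for the interval from vaccination to onset.

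The cost is small: a sentence in section 5, matching wording elsewhere, at most one date field, and a window calculation in REDCap. No visit or assessment is added.

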## **5.1 Schedule for new cases**

### **5.1.1 Baseline visit**

Routine blood work, electrocardiogram, Holter monitor, echocardiogram, MRI. Appendix 8 outlines the schedule of assessments.

### **5.1.2 Follow-up visits**

3-month, 12-month and annual clinical visits with bloodwork to ensure normalization of CRP, troponin, CK. Consider repeat troponin even if previously normalized (to capture recurrence), and repeat electrocardiogram, Holter monitor, echocardiogram or MRI if the initial test was abnormal.

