### 3.4 Secondary endpoints

- Individual components of primary composite endpoint at 30 days and 42 days post vaccination.
- Atrial arrhythmias.
- All-cause and cardiovascular mortality.
- All-cause and cardiovascular hospitalization.
- Recurrence of myocarditis/pericarditis.
- Constrictive pericarditis.

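### Section 5.1.2 and Appendix 8 disagree on follow-up bloodwork, so scheduled biomarker detection of recurrence depends on which one a site follows

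*Protocol*

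**What the plan says.** Section 5.1.2 sets the follow-up of new cases: "3-month, 12-month and annual clinical visits with bloodwork to ensure normalization of CRP, troponin, CK". It attaches no explicit condition to the bloodwork. It then adds "Consider repeat troponin even if previously normalized (to capture recurrence"), and limits the cardiac tests: "repeat electrocardiogram, Holter monitor, echocardiogram or MRI if the initial test was abnormal".

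Section 5 puts follow-up at 3 and 12 months and then yearly for up to 3 years, so the annual visits are those at 24 and 36 months.

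Appendix 8 is the schedule of assessments to which Section 5.1.1 sends sites. Its bloodwork row ("Bloodwork SOC" at baseline) is marked at 3 and 12 months and blank at 24 and 36. Both marks carry a footnote: "repeat diagnostic tests if initial test was abnormal". The row "ECG, Holter, Echo, MRI" carries the same footnote at all four follow-up visits. The clinical symptoms row is marked at baseline only. The rows for events and for outcomes are marked at all four follow-up visits, and Appendix 7 says that outcomes means the primary and secondary endpoints.

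Section 3.4 lists "Recurrence of myocarditis/pericarditis" among the secondary endpoints.

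**The concern.** Both places instruct sites, and they give different instructions for the same blood tests. Section 5.1.2 itself gives the detection of recurrence as the reason for repeating troponin, so the disagreement bears on a listed endpoint and is more than clerical.

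A site working from Section 5.1.2 would draw blood at every annual visit. A site working from Appendix 8 would draw none after 12 months. A recurrence that shows mainly as a raised biomarker could be picked up at the first site's scheduled visit and missed at the second's. Differences in recurrence between sites, or between patient groups spread unevenly over sites, could then partly reflect the schedule used. No analysis plan can recover blood tests that were never taken.

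**Working it through.** No formula applies and the protocol gives no figure to reproduce. The check sets the two schedules side by side, visit by visit.

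| Follow-up visit | Bloodwork, Section 5.1.2 | Bloodwork, Appendix 8 | ECG, Holter, echo, MRI (both places) | Symptoms, Appendix 8 | Events and Outcomes, Appendix 8 |
|---|---|---|---|---|---|
| 3 months | yes, no stated condition | only if initially abnormal | if initially abnormal | no | yes |
| 12 months | yes, no stated condition | only if initially abnormal | if initially abnormal | no | yes |
| 24 months | yes, no stated condition | none | if initially abnormal | no | yes |
| 36 months | yes, no stated condition | none | if initially abnormal | no | yes |

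1. **Timing of bloodwork.** Section 5.1.2 has it at 4 of 4 follow-up visits and Appendix 8 at 2 of 4, so they differ at 4 − 2 = 2 visits, 24 and 36 months. The blanks look intended, since the cardiac-test row of the same table is marked at all four visits.

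2. **Condition on bloodwork.** In Section 5.1.2 the condition of an abnormal initial test is attached to the ECG, Holter, echocardiogram and MRI. In Appendix 8 the footnote also covers bloodwork. At 3 and 12 months the two differ only for patients whose initial test was normal. Even there the conflict is arguable, because checking that a marker has normalized presupposes that it was once abnormal.

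3. **Does the softer reading in step 2 remove the conflict at 24 and 36 months?** No. Suppose Section 5.1.2 meant bloodwork only for patients with an abnormal initial result. Those patients would still have it at the annual visits under Section 5.1.2, and Appendix 8 schedules it for nobody then.

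4. **Repeat troponin.** The instruction is discretionary, so its absence from a table is not by itself a contradiction. Where the initial troponin was the raised one, the footnote permits a repeat at 3 and 12 months. Appendix 8 offers no place for it at 24 or 36 months.

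5. **Symptoms.** Appendix 8 marks them at 0 of 4 follow-up visits. Section 5.1.2 does not mention them. This is an omission in one place, not a disagreement between two.

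6. **Link to the endpoint.** The protocol does not define recurrence. If the Brighton criteria used for diagnosis (Section 4.4) were applied again, troponin would count towards myocarditis Levels 1 and 2 and CRP towards Level 3, and symptoms would be required at Levels 2 and 3 (Appendix 1). Blood markers do not enter the pericarditis levels (Appendix 3). On that assumption the bloodwork conflict bears on recurrent myocarditis, and the symptom gap on both conditions.

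**The case against.** The strongest reply is that little is lost. Appendix 8 collects events and outcomes at every follow-up visit, outcomes include recurrence, and conditional cardiac tests run to 36 months. This stands. A reader might infer from the blank bloodwork cells that recurrence is hardly looked for after 12 months, and the table does not support that: a clinically reported recurrence would be recorded. A reader might also infer that the two places contradict each other on symptoms. They do not, and Section 5 describes the case report form item as symptoms at presentation, which fits a baseline mark.

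A second reply is that uneven testing is built into the study. Section 4.1 joins the active arm to standard care, Section 4.10 limits chart review to data already collected, and Section 5.2 has remote cases rely on investigations already done. This is true, and it confines the point to new cases followed prospectively. For those cases Section 5.1.2 does set a schedule, and variation in routine care is no reason to add more through two conflicting instructions.

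A third reply is that the definition of recurrence may sit in a statistical analysis plan not seen here. That is possible, and it is why the Brighton link is treated as an assumption. The conflict over which tests are done stands whatever the definition.

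**Conclusion.** The concern holds in a limited form. Section 5.1.2 and Appendix 8 contradict each other on bloodwork at 24 and 36 months, two of four follow-up visits. They arguably also do so at 3 and 12 months for patients with a normal initial test. The missing follow-up symptom item is a separate gap.

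The consequence is that scheduled biomarker ascertainment of recurrence in prospectively followed new cases depends on which text a site uses. The effect on the recurrence rate cannot be sized, because the protocol gives no expected rate and no indication of which text sites follow.

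No primary endpoint is touched. MACE is assessed at 30 and 42 days (Section 3.3), before the first follow-up visit; recovery of cardiac function rests on ejection fraction, and the two places agree on imaging; the questionnaires are scheduled at every visit. Of the six items in Section 3.4, the one at issue is recurrence. This should be corrected, but it does not threaten the study's main results.

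**What to change.** - Reconcile Section 5.1.2 and Appendix 8 into one bloodwork schedule for all sites, stating at which visits it applies and whether it depends on the initial result. Which schedule is right is for the sponsor to decide.
- Record symptoms on the existing follow-up form and mark the row accordingly in Appendix 8.
- Report the number of patients tested at each visit alongside the recurrence rate, so that a reader can separate low recurrence from little testing. Keep counting recurrences diagnosed between visits or found by chart review; restricting the endpoint to scheduled-visit data would discard real events.

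The cost is an amendment to one paragraph or one table, one form item, and one line of reporting. Some uneven testing will remain, because remote and chart-review cases depend on tests already done; the report should say so.
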